## 4.6 Steering Committee

A Steering Committee will be established for this study. The Steering Committee will consist of investigator participating in the study, an additional study physician, and a

statistician. Study design and inclusion/exclusion/withdrawal criteria will be determined by the Steering Committee.

Members of the Steering Committee will periodically review the status of enrolled patients and adjudicate on situations not covered by existing inclusion, exclusion, or withdrawal criteria.

## 4.7 Independent Data Monitoring Committee

The Independent Data Monitoring Committee (IDMC) will review the trial data to monitor the quality of trial operations, including the protocol compliance, recruitment status, dropout rate, and data integrity. The IDMC will monitor the accumulated patient safety data every 1 month upon request. The IDMC may propose recommendations on adjustment of the ongoing trial design on the premise of ensuring the integrity of the trial.

## 4.8 Study Termination

EOS is defined as the last patient last visit at the end of the follow-up period, which will be the last data collection point and the last patient may be an outpatient or laboratory sample. EOS is expected to occur approximately 2 years after enrollment of the last patient. A patient will be considered to have completed the study if he/she dies or meets any of the withdrawal criteria.

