## 4. Study Design

## 4.1 Overall Study Design

This is a prospective multicenter Phase II clinical study employing an oral regimen administered in 3-month cycles. Patients will receive thalidomide of 50 to 100 mg QD before bedtime, prednisone of 0.5 to 1.0 mg/kg QOD, methotrexate of 10 mg/m²/week for up to 4 cycles. Prednisone will be tapered after 3 months. Patients who achieve CR can discontinue methotrexate after 4 months of consolidation therapy, with a maximum duration of 1 year. For patients who achieved a partial remission (PR) or CR, Thal maintenance therapy was recommended to be continued for a maximum duration of two years, but also depended on patients or investigator's choices.

Efficacy evaluation will be conducted at the end of each cycle starting from Cycle 1. The efficacy evaluations will continue until PD, discontinuation of treatment (for patients who continue treatment after PD), initiation of a new anti-cancer therapy, or withdrawal from the study (eg, death, patient's request, loss of follow-up, etc.), whichever occurs first.

The primary objective of this study is to evaluate the efficacy and safety of TPM regimen and further explore the biomarkers associated with clinical efficacy.

Abbreviations: CR, complete remission; MTX, methotrexate; Pred, Prednisone; Thal, thalidomide.

Notes:

Thal: 50 to 100 mg, oral, before bed, for 2 years;

Pred: 0.5-1 mg/kg, oral, every other day, could be tapered after 3 months of dosing and dosed for up to 6 months

MTX: 10 mg/m^2, once weekly, patients who achieve CR can discontinue MTX after 4 months of consolidation therapy, with a maximum duration of 1 year.

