## 4.4 Follow-up

Patients who withdraw from the study due to intolerable AEs will be followed up in this study until the events resolve to Grade 1 or lower, or the AE is stable. Patients will be followed up for up to 24 months after completion of the treatment, or until study termination, PD, initiation of new anti-tumor therapy, or death.

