#### 5.3 Withdrawal Criteria

- 1. Patients withdraw the ICFs
- 2. Patients experience PD or death
- 3. Patients experience intolerable toxicity that cannot be relieved after symptomatic treatment
- 4. Patients are unwilling to continue treatment
- 5. There was no clinical benefit for more than half a year
- 6. Delayed dosing for more than 4 weeks and patients are judged by investigators to be unsuitable for further dosing

- 7. Pregnancy
- 8. Lost to follow-up
- 9. Treatment should be discontinued based on the best interests of the patients at the investigator' discretion
- 10. Patients does not comply with the protocol, and the investigator deems it necessary to discontinue the treatment
- 11. The collaborator or regulatory authority notifies to end the clinical study.

If treatment discontinuation is due to any of the above reasons, the investigator must notify the Principal Investigator and complete the case summary page in the case report form (CRF), along with the date and reason for the treatment discontinuation. If treatment discontinuation is due to an AE, the AE will be followed up until it is resolved and stable.

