# 5.4 Removal of Patients from Therapy or Assessment

Efforts must be made to complete the efficacy and safety tests at the time of treatment discontinuation as specified in the protocol, and to complete safety follow-up, with complete documentation of AEs and outcomes. The investigator may recommend or provide new or alternative treatments to the patient according to the actual conditions. Patients with non-PD should continue to be followed up for efficacy evaluation until they start a new antineoplastic therapy or have PD.

If a patient refuses to visit the study site for further visits, he/she should continue to be followed up for the collection of information about the study unless he/she withdraws consent to disclose further information or be contacted. In this case, no further evaluation should be conducted and no further information should be collected.

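### Sections 4.8 and 4.1 can be read as ending disease assessment when a patient stops treatment without progression, while 5.4, 8.4 and 8.5.1 continue follow-up; PFS and DoR need one rule

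*Supplement*

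**What the plan says.** All references are to protocol version 2.0.

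**Text that ends participation**
- 4.8: "A patient will be considered to have completed the study if he/she dies or meets any of the withdrawal criteria".
- 5.3 lists those criteria. Several need no progression, for example criterion 3, "Patients experience intolerable toxicity that cannot be relieved after symptomatic treatment", and criterion 4, "Patients are unwilling to continue treatment". Criteria 5 (no clinical benefit), 6 (dosing delay), 7 (pregnancy), 9 (investigator's decision) and 10 (non-compliance) are of the same kind.
- 4.1 lists the events that end efficacy evaluation. The last is "withdrawal from the study (eg, death, patient's request, loss of follow-up, etc.), whichever occurs first". The same sentence stands in the Synopsis and in 2.6.1.

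**Text that continues follow-up**
- 5.4: "Patients with non-PD should continue to be followed up for efficacy evaluation until they start a new antineoplastic therapy or have PD".
- 8.4 requires a full assessment three months after the last treatment, then twice-yearly follow-up to the end of study that includes disease status.
- 8.5.1 expressly includes patients who stop early for intolerance.

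**Mixed text**
- 4.4 begins "Patients who withdraw from the study due to intolerable AEs will be followed up in this study until the events resolve to Grade 1" and goes on to a general follow-up of up to 24 months after treatment.
- 5.3 is headed as withdrawal criteria, but its closing paragraph treats the same list as reasons for stopping treatment: "If treatment discontinuation is due to any of the above reasons, the investigator must notify the Principal Investigator".

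Section 9.2 defines PFS and DoR without a censoring rule. Section 11.3 leaves the rules to a SAP that is not shown, and that deferral is not at issue here.

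**The concern.** Stopping the drugs and leaving the study are different events, and the protocol uses one list for both. A patient who stops at month 5 for toxicity, without progression, is finished under 4.8 with 4.1. Under 5.4 and 8.4 the same patient is still under disease assessment. Two sites could therefore handle identical patients differently, and each could point to the protocol.

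If assessments end at stopping, the analysis can only censor the patient at the last assessment. That is harmless if stopping says nothing about later progression. If patients who stop early progress sooner, their progressions are never seen and the Kaplan-Meier curve is too high. For a treatment of limited duration, how long remission lasts after the drugs are stopped is much of what PFS and DoR are meant to show.

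The summary of changes for version 2.0 suggests that exits do cost data. It explains the removal of TTNT by noting that patients are withdrawn at progression and that some are then lost. That remark concerns exits at progression, so it is only indirect evidence for the patients discussed here.

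**Working it through.** The plan gives no figure on this point, so none can be reproduced. The check has two parts.

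**1. The rules applied to one patient who stops at month 5 for toxicity, without progression**
- 5.3, criterion 3 is met.
- 4.8: the patient has completed the study.
- 4.1: if that counts as withdrawal from the study, efficacy evaluation ends. Stopping treatment does not end it by itself, because that limb of 4.1 is confined to patients treated beyond progression.
- 4.4: the AE is followed until it resolves or is stable, and the general 24-month follow-up may or may not apply.
- 5.4, 8.4 and 8.5.1: disease assessment continues.

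The last assessment is therefore near month 5 on one reading. On the other it is at progression, new therapy or the end of follow-up.

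**2. Size of the difference at 24 months**

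From 4.5: 42 enrolled, 35 needed, 20% dropout. That is 42 − 35 = 7 patients, or 0.20 × 42 = 8.4. The share who stop without progression is not given.

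Assumptions, none of them in the documents:
- 24-month PFS on the full regimen is S = 0.70 or 0.80, with constant hazard h = −ln(S)/24.
- A share d = 0.20 stops, at a time u uniform over months 1 to 12, if still progression-free. This assigns the whole dropout allowance to such patients.
- After stopping, the progression hazard is r × h, with r = 1, 2 or 3.

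Censored at stopping, Kaplan-Meier estimates S, because everyone still at risk has hazard h. With continued follow-up, 24-month PFS is

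(1 − d)·S + d·S·E, where E = [exp(−12k) − exp(−23k)] / (11k) and k = (r − 1)·h.

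E is the average of exp(−k(24 − u)) over u from 1 to 12.

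| S | h | r | E | PFS with follow-up | Overstatement if censored |
|---|---|---|---|---|---|
| 0.70 | 0.01486 | 2 | 0.772 | 0.560 + 0.108 = 0.668 | 3.2 points |
| 0.70 | 0.01486 | 3 | 0.597 | 0.560 + 0.084 = 0.644 | 5.6 points |
| 0.80 | 0.00930 | 2 | 0.850 | 0.640 + 0.136 = 0.776 | 2.4 points |
| 0.80 | 0.00930 | 3 | 0.724 | 0.640 + 0.116 = 0.756 | 4.4 points |

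At r = 1, E = 1 and the difference is zero.

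A simulation of the same set-up (42 patients, 3,000 runs per case, stoppers followed for 24 months after stopping) gives 3.2, 5.6, 2.3 and 4.5 points in the same order. The standard error of 24-month PFS is about 7 to 8 points in the 70% case and 6 to 7 in the 80% case. Mean PFS events, with stoppers censored and then followed at r = 1, 2, 3:
- 70% case: 17.9 against 20.2, 21.9, 22.9
- 80% case: 12.5 against 14.1, 15.4, 16.4

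About 3 to 5 events are lost at r = 2 to 3. At r = 1 there is no bias, but about 11% of events are lost (2.3 of 20.2). The standard error then rises from about 7.1 to 7.8 points in the 70% case.

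**Sensitivity**
- If half of the stoppers start new therapy at once, which ends follow-up under 5.4 as well, the overstatement falls to 1.3–1.8 points (r = 2) or 2.5–3.2 points (r = 3).
- If in addition only 10% stop, it is 0.6–1.5 points across r = 2 to 3.

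**The case against.** The sections that govern visits already settle the matter. Sections 5.4, 8.4 and 8.5.1 all require follow-up of patients who stop early, and 8.4 names disease status. Against them, 4.8 reads as an accounting sentence that mentions neither assessments nor censoring, and 4.4 continues to a general 24-month follow-up. A site working from the visit schedule would keep assessing. This stands in part. Most of the procedural text is on one side, so 4.8 and 4.1 are the outliers. It does not remove the conflict, because 4.1 is the design statement of when efficacy evaluation ends.

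Three stronger readings are tempting, and the documents do not support them:
- A reader might infer that the plan censors PFS and DoR at stopping. No section says so. The examples in the PFS definition in 9.2 mention toxicity and unrecorded progression in a new treatment. They are ambiguous and could even be read as counting such cases as events.
- A reader might infer that 5.3 itself makes these events study completion. It does not. Its closing paragraph speaks of treatment discontinuation, and only 4.8 speaks of completion.
- A reader might take the 20% as the rate of stopping without progression. It is a dropout allowance, and it can include loss to follow-up and withdrawal of consent, which are unobserved on either reading. For criterion 5, 6.1 moves patients to second-line treatment, where 5.4 also ends follow-up, so the readings largely agree.

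It is also true that every scenario in the main table lies below one standard error, and that PFS and DoR are summarised descriptively.

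**Conclusion.** The point holds as a contradiction in the current text. The protocol is wrong as written on when disease assessment ends for a patient who stops treatment without progression. Censoring at stopping is a consequence of following 4.8 with 4.1, not a stated rule. A later SAP can choose how to analyse assessments, but it cannot supply ones that were never made.

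The effect is modest and conditional. With the full 20% as non-progression stoppers, 24-month PFS would be overstated by about 2 to 3 points if stopping doubles the progression hazard and by about 4.5 to 5.6 points if it triples it, against a standard error of about 6 to 8 points. The overstatement is smaller if fewer stop or if some start new therapy at once, and it is zero if the hazard does not change. The hazard ratios, stopping times and PFS levels are assumptions. Only secondary endpoints are concerned, and no effect on the primary CRR is claimed. The change is still worth making, because it removes a possible source of informative censoring at almost no cost.

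**What to change.** Reconcile 4.1, 4.4, 4.8 and 5.3 with 5.4, 8.4 and 8.5.1 by separating discontinuation of treatment from withdrawal from the study.

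- **4.8:** limit study completion to death, withdrawal of consent to follow-up, loss to follow-up, study termination, or the end of the 24-month follow-up. Refer to 4.4 and 5.4 for progression and new therapy as the events that end disease assessment, so that the lists agree.
- **5.3 (and the Synopsis list):** label criteria 3 to 7, 9 and 10 as discontinuation of treatment. Refer to 5.4 for disease assessment until progression or new antineoplastic therapy.
- **4.1 (and the same sentence in the Synopsis and 2.6.1):** state that withdrawal from the study means withdrawal of consent to follow-up, not stopping treatment.
- **4.4:** limit the AE sentence to follow-up of the AE, so that it does not appear to replace the general follow-up.
- **SAP:** make the PFS and DoR censoring rules match.

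The cost is amendment wording and a few more follow-up visits for patients who stop early, which 8.4 and 8.5.1 already schedule. No rule on when treatment is stopped is changed.

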## 5 Study Population

Eligible patients will be screened within 28 days prior to the administration of the study drugs. Refer to Section 5.5, Screen Failures, for conditions that allow any screening procedure to be repeated.

The inclusion and exclusion criteria for patients enrolled in this study are summarized below. If there is any doubt about these criteria, the investigator must consult with the Sponsor representative and resolve all issues prior to study enrollment. No exemptions are allowed.

## 5.1 Eligibility Criteria for Prescreening

- 1. Sign pre-screening informed consent form (ICF).
- 2. Willing to provide a tumor tissue sample (archived or recently collected) for tumor genetic analysis.

## 5.2 Inclusion and Exclusion Criteria

#### 5.2.1 Inclusion Criteria

- 1. Patients who fulfill the diagnostic criteria for T-LGLL or CLPD-NK specified in the 2016 WHO Classification of Lymphoid Neoplasms [1]
- 2. Patients are fully informed about the study and willing to participate in the study and provide written ICF
- 3. Male or female, aged  $\geq$ 18 years
- 4. Treatment-naive patients, or patients treated with or relapsed from a non-methotrexate/ thalidomide-based regimen
- 5. Patients with at least one of the following indications for LGLL treatment:
  - a. ANC  $<0.5 \times 10^9$ /L, or neutropenia with recurrent infections
  - b. Hemoglobin <100 g/L, or requiring infusion of red blood cells
  - c. Platelets level  $< 50 \times 10^9 / L$
  - d. Concomitant autoimmune diseases requiring treatment
  - e. Symptomatic splenomegaly
  - f. Severe B symptoms (fever of unknown cause with body temperature over 38 °C; night sweats; weight loss of ≥10% within half a year)
  - g. Pulmonary hypertension
- 6. Patients with Eastern Cooperative Oncology Group (ECOG) score of 0 to 2 (Appendix 1)
- 7. Patients with life expectancy  $\geq 6$  months.

#### 5.2.2 Exclusion Criteria

- 1. Patients not diagnosed with T-LGLL or CLPD-NK
- 2. Patients with no indication for LGLL treatment
- 3. Patients who are unable to understand or follow study procedures
- 4. Patients who have been diagnosed or treated for malignancies other than LGLL within the past five years
- 5. Patients with non-lymphoma-related hepatic and renal impairment: alanine aminotransferase (ALT)  $> 3 \times$  upper limit of normal (ULN), aspartate aminotransferase (AST)  $> 3 \times$  ULN, total bilirubin  $> 2 \times$  ULN, and serum creatinine clearance (CrCl) < 30 mL/min
- 6. Patients with other severe diseases that have an impact on this study (uncontrolled diabetes, stomach ulcers, other severe cardiopulmonary conditions, etc.), at the discretion of investigators.
- 7. High-risk patients based on the Caprini score for thromboembolism (Appendix 2)
- 8. Patients with a known history of HIV infection, or with active hepatitis B virus (HBV) infection, or any uncontrolled active systemic infection requiring intravenous antibiotics

Notes: HBV infection is considered active if all following criteria are met: a. HBV DNA quantification ≥2000 IU/mL; b. ALT ≥2 times × ULN; c. LGLL, medications, and other causes-induced hepatitis are excluded. Patients with active HBV infection at the time of initial diagnosis who are converted to inactive HBV infection after adequate anti-HBV treatment could be enrolled in this study.

- 9. Patients who have undergone major surgery (excluding lymph node biopsy) within the past 14 days or who are expected to undergo major surgery during study treatment
- 10. Pregnant or lactating women, and women of childbearing potential who have not taken contraceptive measures
- 11. Patients who are allergic to the agents or the ingredients

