#### **Exclusion Criteria:**

- 1. Patients not diagnosed with T-LGLL or CLPD-NK
- 2. Patients with no indication for LGLL treatment
- 3. Patients who are unable to understand or follow study procedures
- 4. Patients who have been diagnosed or treated for malignancies other than LGLL within the past five years
- 5. Patients with non-lymphoma-related hepatic and renal impairment: alanine aminotransferase (ALT)  $> 3 \times$  upper limit of normal (ULN), aspartate aminotransferase (AST)  $> 3 \times$  ULN, total bilirubin  $> 2 \times$  ULN, and serum creatinine clearance (CrCl) <30 mL/min
- 6. Patients with other severe diseases that have an impact on this study (uncontrolled diabetes, stomach ulcers, other severe cardiopulmonary conditions, etc.), at the discretion of investigators.
- 7. High-risk patients based on the Caprini score for thromboembolism (Appendix 2)
- 8. Patients with a known history of HIV infection, or with active hepatitis B virus (HBV) infection, or any uncontrolled active systemic infection requiring intravenous antibiotics

Notes: HBV infection is considered active if all following criteria are met: a. HBV DNA quantification ≥2000 IU/mL; b. ALT ≥2 times × ULN; c. LGLL, medications, and other causes-induced hepatitis are excluded. Patients with active HBV infection at the time of initial diagnosis who are converted to inactive HBV infection after adequate anti-HBV treatment could be enrolled in this study.

- 9. Patients who have undergone major surgery (excluding lymph node biopsy) within the past 14 days or who are expected to undergo major surgery during study treatment
- 10. Pregnant or lactating women, and women of childbearing potential who have not taken contraceptive measures
- 11. Patients who are allergic to the agents or the ingredients

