After oral administration of methotrexate, its absorption occurs in the proximal jejunum, mainly through the proton-coupled folate transporter (PCFT/SLC46A1), which transports reduced folic acid and methotrexate. In addition, part of methotrexate may be metabolized to 4-amino-4-deoxy-N10-methylpara aminobenzoic acid with the involvement of intestinal bacteria. The bioavailability of methotrexate is relatively high, generally in the range of 64% to 90%, but varies widely between patients and decreases with increasing doses, with stable bioavailability at doses greater than 15 mg per week, indicating intestinal transporter saturation. Methotrexate, when taken orally, has a Cmax of between 0.3 to 1.6 µmol/L, generally occurring 0.75 to 2 hours after administration. Multiple studies have demonstrated that subcutaneous injection of methotrexate has higher bioavailability compared with oral methotrexate. Subcutaneous injection of methotrexate resulted in linear, dose-proportional increases in blood drug concentrations, with no dose saturation effect. Approximately 50% of circulating methotrexate binds to plasma protein. Methotrexate can be distributed into synovial fluid at concentrations comparable to those in plasma. Methotrexate undergoes the firstpass effect metabolism in the liver and is converted to 7-hydroxymethotrexate (7-OH-MTX), a major metabolite of methotrexate. Renal excretion is the main route of excretion for methotrexate. Methotrexate is filtered through the glomeruli, as well as active tubular secretion and reabsorption. A small portion of methotrexate is excreted through bile and a portion enters hepatic-enteric circulation. The plasma half-life of low dose of methotrexate is between 4.5 to 10 hours. The excretion of methotrexate is reduced in patients with impaired renal function, ascites, or pleural effusion, who need to be particularly careful to monitor toxic effects and may need to reduce the dose or in some cases discontinue methotrexate therapy.

Cellular uptake of methotrexate is mediated by reduced folate carrier 1 (RFC1/SLC19A1), with limited contributions from  $\alpha$  and  $\beta$  folate receptors. The

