## 7.4.2 Dose Adjustment and Discontinuation of Methotrexate

Methotrexate is contraindicated in LGLL patients with an estimated glomerular filtration rate (eGFR) <30 mL/min. For patients with an eGFR of 30 to 59 mL/min, a lower initial dosage is required; and a more gradual dose increase, close monitoring, and a lower maximum weekly dose should be considered, depending on the overall clinical conditions. Although low doses of methotrexate are not nephrotoxic, methotrexate is almost completely excreted through the kidney. Therefore, kidney function should be monitored. If renal insufficiency occurs, the methotrexate dose should be reduced or discontinued.

Guidelines from Cancer Care Ontario in Canada recommend a 25% reduction of dose at CrCl of 80 mL/min, 40% reduction at CrCl of 60 mL/min, 50% reduction at CrCl of 50 mL/min, and discontinuation at CrCl <50 mL/min. The guidelines also state that less conservative dose adjustments may be considered when using a low-dose regimen (<50 mg/m²). High-dose methotrexate could only be administered only when CrCl is >60 mL/min.

See Appendix 2 for the calculation method of CrCl.

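### Exclusion 5 does not exclude disease-related creatinine clearance below 30 mL/min, although Section 7.4.2 bars methotrexate at that level whatever the cause

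*Supplement*

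**What the plan says.** Exclusion 5 appears in the synopsis and in Section 5.2.2 with the same qualifier. It opens with "Patients with non-lymphoma-related hepatic and renal impairment" and then lists limits for ALT, AST, total bilirubin and "serum creatinine clearance (CrCl) <30 mL/min". No other criterion sets a renal limit. Section 5 adds "No exemptions are allowed".

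Section 7.4.2 states "Methotrexate is contraindicated in LGLL patients with an estimated glomerular filtration rate (eGFR) <30 mL/min", with no condition on cause. For moderate impairment it continues: "For patients with an eGFR of 30 to 59 mL/min, a lower initial dosage is required". Its first paragraph ends by calling for dose reduction or discontinuation if renal insufficiency develops.

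The second paragraph reports the schedule of an outside Canadian guideline, which includes "50% reduction at CrCl of 50 mL/min, and discontinuation at CrCl <50 mL/min". It then says that under the same guideline "less conservative dose adjustments may be considered when using a low-dose regimen", meaning below 50 mg/m². The section closes by referring to Appendix 2 for the CrCl calculation. In version 2.0, Appendix 2 is the Caprini thrombosis form, and the Cockcroft-Gault formula is in Appendix 3.

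**The concern.** The entry rule and the dosing rule use the same number, 30 mL/min, but differ on cause. Section 2.5 describes LGLL as an indolent lymphoma, so the qualifier in exclusion 5 reads as exempting impairment due to the study disease. That may suit liver enzymes raised by the disease. It has no stated basis for a drug cleared by the kidney. The pharmacology in Section 2.4 rests on clearance: "The excretion of methotrexate is reduced in patients with impaired renal function, ascites, or pleural effusion". Section 7.4.2 likewise says that elimination is almost entirely renal.

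At stake is the enrollment of a patient who cannot receive the regimen under study. The primary endpoint in Section 9.3 is the complete remission rate in patients given all three drugs.

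**Working it through.** The plan gives no figure to reproduce. The check sets the renal rules side by side, treating eGFR and CrCl as equal. That is an assumption, since the protocol does not link them.

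**Below 30 mL/min**

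- Not disease-related: excluded by criterion 5, and methotrexate contraindicated by Section 7.4.2. Consistent.
- Disease-related: not excluded by criterion 5, yet methotrexate contraindicated by Section 7.4.2. Inconsistent.

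In the second case the methotrexate dose is 0 of the planned 10 mg/m² per week, so at most 2 of the 3 drugs can be given.

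**Number of patients.** Sections 2.1 and 2.2 describe the disease and list the indications for treatment. Neither mentions renal failure caused by LGLL, and the documents give no distribution of renal function. With an assumed 0 to 1 such patients and the 42 planned in Section 4.5: 0/42 = 0% and 1/42 = 2.4%.

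**Where the limit falls.** Appendix 3 gives CrCl = 1.222 × (140 − age) × weight / creatinine in µmol/L, times 0.85 for women. The calculation below solves for creatinine at CrCl 30. Age is 60, the median age of onset in Section 2.1, and the weights are assumed.

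- Woman, 50 kg: 1.222 × 80 × 50 × 0.85 / 30 = 4154.8 / 30 = 138 µmol/L
- Woman, 60 kg: 4985.8 / 30 = 166 µmol/L
- Man, 70 kg: 6843.2 / 30 = 228 µmol/L
- Man, 80 kg: 7820.8 / 30 = 261 µmol/L

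These values only locate the threshold. They do not measure the defect.

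**From 30 to 49 mL/min (minor).** The patient is eligible. The protocol's own rule requires a lower starting dose, while the quoted guideline says to stop unless relaxed for low-dose use. The trial dose of 10 mg/m² is below 50 mg/m², so the relaxation can apply. The text does not say whether the schedule binds in this trial.

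**Measure and pointer.** Section 7.4.2 states its own limits as eGFR, while exclusion 5 and the guideline schedule use CrCl. The only formula supplied is for CrCl. The Section 7.4.2 pointer to Appendix 2 is out of date, whereas the pointer in Section 7.4.1 to the neurotoxicity table (Appendix 4) is correct.

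**The case against.** The strongest reply is that the gap may contain nobody, and that other provisions would catch anyone in it.

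- Section 5 requires doubts about eligibility to be settled with the sponsor before enrollment, and a contraindicated study drug is an obvious doubt.
- Exclusion 6 lets the investigator exclude other severe disease that affects the study.
- The ban on exemptions stops ineligible patients from being let in. It does not oblige a site to enroll everyone who is not excluded.
- Section 7.4.2 itself stops the methotrexate.

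All of this stands as a limit on the consequence. None of it changes the stated rule: these safeguards rest on discretion or consultation, and the criterion and the contraindication still disagree.

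A reader might go further and infer that Section 7.4.2 gives sites conflicting orders at 30 to 49 mL/min. The documents do not support that. The schedule is attributed to an outside body and softened for low doses, while the protocol's own rules are worded as directives. Once treatment has started, the first paragraph already allows either reduction or discontinuation, so the tension concerns the starting dose only.

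A reader might also infer that mixing eGFR and CrCl sorts patients differently. No such patient can be shown from the documents: entry and contraindication share the number 30, and only one formula is given. The appendix number is an editorial slip, since the correct appendix follows directly and is clearly titled.

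**Conclusion.** The point holds for eligibility. As written, exclusion 5 does not exclude disease-related CrCl below 30 mL/min, and Section 7.4.2 contraindicates methotrexate there regardless of cause. This is a contradiction in the wording of version 2.0 and should be corrected.

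Its practical size is small: 0 to 2.4% of the planned sample if 0 to 1 such patients are assumed, with zero quite possible. The reading assumes that lymphoma-related means related to LGLL, as the description in Section 2.5 suggests.

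It would be wrong to infer that the protocol directs an unsafe dose, because Section 7.4.2 forbids methotrexate below 30. Nor do the documents support any claim about the complete remission rate. The choice of renal measure, the appendix pointer and the status of the guideline are tidying points.

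**What to change.** - In the synopsis and Section 5.2.2, make CrCl below 30 mL/min from any cause a separate, unconditional exclusion. The cause qualifier can stay on the hepatic limits.
- In Section 7.4.2, use Cockcroft-Gault CrCl as the renal measure and change the reference from Appendix 2 to Appendix 3.
- As a minor clarification, label the quoted guideline schedule as background or delete it. This removes the stop-below-50 wording that sits beside the protocol's lower starting dose at 30 to 59 mL/min. It will not by itself standardize dosing in that band, because the protocol gives no amount for the lower dose. Whether to add numeric doses is for the sponsor's clinicians.

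The cost is amendment text only. Weight and creatinine are already collected at screening (Section 8.1), and creatinine again during Months 1 to 24 (Section 8.2), so no new test is needed. The downside is that a rare extra patient may be excluded, who could not have received methotrexate anyway.
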